9.4. Deaths, Serious Adverse Events, and Other Significant Adverse Events

A serious adverse event is an adverse event that fulfills the following criteria:

- Is fatal (results in death);
- Is life-threatening (Note: the term "life-threatening" refers to an event in which the patient was at risk of death at the time of the event; it does not refer to an event that could hypothetically have caused death had it been more severe);
- Requires inpatient hospitalization or prolongation of existing hospitalization (hospitalization is defined as an inpatient admission, regardless of length of stay);
- Results in persistent or significant disability/incapacity (a substantial disruption of the patient's ability to conduct normal life functions);
- Is a congenital anomaly/birth defect; or
- Constitutes an important medical event that may jeopardize the patient or may require medical or surgical intervention to prevent one of the other outcomes listed above.

Serious adverse events will be summarized according to Section 9.3.

By-patient listings will be provided for any deaths, serious adverse events, and adverse events leading to discontinuation of treatment. Treatment-emergent adverse events that result in dose interruption will also be identified.

9.5. Clinical Laboratory Evaluation

Clinical laboratory samples should be collected at the beginning of each clinic visit and just prior to a dose on all Study Visit Days and will be processed by a central laboratory. In the event a patient is unable to attend an in-clinic visit due to COVID-19, clinical laboratory blood draws may be performed by a Home Health Care agency or a local laboratory.

Clinical laboratory variables will be presented in 3 ways. First, change from baseline to the minimum post-baseline value, maximum post-baseline value, and final on-treatment value will be summarized. Baseline will be defined as the laboratory value obtained before the first dose of study drug on Day 1; if Day 1 values are unavailable, then values obtained at the Screening Visit will be used. Only post-baseline values on treatment will be eligible. The Follow-up Visit will be excluded from possible minimum, maximum, or final post-baseline values.

This analysis will be repeated with outlying values removed from eligibility for minimum and maximum values. An outlier is defined using the interquartile range (IQR). The IQR is equal to the third quartile minus the first quartile and will be calculated by visit and treatment group for each numeric parameter. The IQR will be multiplied by a constant of 1.5. Any value which is above 1.5 times IQR plus the third quartile or below 1.5 times IQR minus the first quartile will be considered an outlier and will be removed from eligibility for minimum, maximum, or final post-baseline values.

Second, shift tables will summarize the number and percentage of patients with categorical changes from baseline defined by the laboratory normal reference range for each laboratory parameter (Below reference range, Within reference range, and Above reference range). The baseline category will be cross-tabulated with post-baseline category (3×3 table). The post baseline category will be assigned and summarized in 2 ways for each laboratory parameter: minimum post-baseline value and maximum post-baseline value. Only post-baseline values on treatment will be eligible. Patients will only be reported in the shift tables if they have both a baseline and post-baseline value.

Third, treatment-emergent potentially clinically significant (PCS) laboratory values will be identified. PCS values are defined as those that meet Grade 3 or Grade 4 toxicity criteria from the Common Terminology Criteria for Adverse Events (CTCAE) criteria. Laboratory values will be graded using CTCAE version 5.0, for those values included. CTCAE grades will be based solely on numeric results and without regard to other symptoms based on clinical judgment. For laboratory parameters whose CTCAE grading is independent of baseline criteria, treatment-emergent PCS laboratory values are those in which the baseline value is not PCS and the post-baseline value is PCS. For laboratory parameters whose CTCAE grading is dependent upon baseline criteria, any post-baseline grading of Grade 3 or Grade 4 will be considered treatment-emergent. The number and percentage of patients with treatment-emergent PCS laboratory values will be summarized by treatment group for each clinical laboratory variable.

These analyses will be repeated for serum chemistry results, hematology results, and lipid results (where lipid tests include total cholesterol, low-density lipoprotein, high-density lipoprotein,

triglycerides). Laboratory results will also be listed. Reference ranges for each clinical laboratory parameter will also be summarized in a data listing.

Box plots of hemoglobin, platelets, and neutrophils will also be provided with dose interruption limits included as reference lines (see Protocol Section 9.2.1).

Pregnancy test results will be listed only.

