Statistical Analysis Plan – CP543.3001

[figure not shown]
- The values that will be MNAR for the MNAR sensitivity analysis are study discontinuations due to TEAEs or lack of efficacy. These values will be imputed using the control arm. As such, adjusting these values would shift those patients to be worse than placebo. As placebo in this study is a true placebo, this is not a realistic or informative shift.
- The protocol states, “Missing values will not be imputed for efficacy endpoints which are not derived from SALT scores.” The SAP adds multiple imputation for the SPRO endpoints because SPRO at Week 24 is an alpha-controlled key secondary endpoint and the treatment of missing data should align with the treatment of missing data for the other alpha-controlled endpoints.
- Protocol Section 12.4.7 Safety
 - Adverse Events
 - The protocol states that “Proportions for adverse events that are gender-specific (e.g., dysmenorrhea) will be based on the number of patients from that gender.” The SAP specifies that the proportion of adverse events will be based on the number of patients in the safety population, even gender-specific adverse events. This change is in line with previous studies in this program and generally accepted conventions.
 - Clinical Laboratory
 - A 4th presentation of labs was added to the SAP in light of outliers seen in blinded data review throughout the study.
- Other changes:
 - Analyses for COVID-19 were added in Section 11 of the SAP.

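### The laboratory outlier rule in SAP 9.5 writes its lower limit with the subtraction reversed, so the filtered minimum/maximum table, coded as written, screens the wrong low values

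*SAP*

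**What the plan says.** SAP Section 9.5 first summarises change from baseline to the minimum, maximum and final on-treatment value of each laboratory variable. It then adds a second version: "This analysis will be repeated with outlying values removed from eligibility for minimum and maximum values". The ingredients of the outlier rule are given in order:

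- "The IQR is equal to the third quartile minus the first quartile and will be calculated by visit and treatment group for each numeric parameter".
- That spread is then scaled by a factor of 1.5.
- An outlier is "Any value which is above 1.5 times IQR plus the third quartile or below 1.5 times IQR minus the first quartile".
- Such a value "will be considered an outlier and will be removed from eligibility for minimum, maximum, or final post-baseline values".

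SAP Section 13 gives the reason for the extra table: "A 4th presentation of labs was added to the SAP in light of outliers seen in blinded data review throughout the study". It names no analyte and does not say whether the outliers were high or low. No other part of either document restates or corrects the rule.

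**The concern.** The paragraph uses the word minus in its ordinary order when it defines the IQR as Q3 − Q1. Read in the same way, the lower limit is 1.5 × IQR − Q1. The upper limit in the same sentence is the standard fence, so the lower one should be its mirror image, Q1 − 1.5 × IQR. The terms have been swapped.

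Coded as written, the table does not do its job on the low side. For variables with a modest spread it screens out no low value. For strongly right-skewed variables it can discard ordinary low values, which moves the change to minimum (and perhaps to final) upward. Low values matter in this trial: Protocol Table 3 sets low-side dose-interruption thresholds for neutrophils, haemoglobin and platelets.

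There is also a conflict of scope. The opening sentence of the paragraph removes outliers for the minimum and maximum only; the closing sentence adds the final value.

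**Working it through.** The plan states no numerical result for this rule, so there is nothing to reproduce first. The check is algebra, followed by illustrations.

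**Inputs from SAP 9.5.** IQR = Q3 − Q1, the multiplier 1.5, and the two limits as worded. The documents give no laboratory quartiles, so every quartile or distribution below is an assumption.

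**Step 1: the two lower limits.** Let r = Q3/Q1 with Q1 > 0, so IQR = Q1(r − 1).

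- Written: 1.5 × IQR − Q1 = Q1(1.5r − 2.5)
- Matching: Q1 − 1.5 × IQR = Q1(2.5 − 1.5r)

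One is exactly the negative of the other.

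**Step 2: what follows for a non-negative variable, whatever its distribution.**

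- 1.5r − 2.5 ≤ 0 when r ≤ 5/3. The written limit is zero or negative, so no low value can be flagged.
- When r > 5/3 the matching limit is negative and flags nothing, but the written limit is positive.
- 1.5r − 2.5 > 1 when r > 7/3. The written limit is above Q1, so at least 25% of values are removed.
- 1.5r − 2.5 > r when r > 5. The written limit is above Q3, so at least 75% are removed.

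**Step 3: two variables with modest spread (assumed quartiles).**

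| Variable | Q1, Q3 | r | 1.5 × IQR | Written limit | Matching limit |
|---|---|---|---|---|---|
| Haemoglobin, g/dL | 13, 15 | 1.15 | 3 | 3 − 13 = −10 | 13 − 3 = 10 |
| Platelets, ×10⁹/L | 220, 300 | 1.36 | 120 | 120 − 220 = −100 | 220 − 120 = 100 |

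The written rule can flag no low value in either. A simulation agrees. For a normal variable with mean 14 and SD 1.2 (1,000,000 draws), the limits are −10.77 and +10.77, and the low-side shares flagged are 0% and 0.36%. A value of 7.0 planted among 209 such draws is kept by the written rule and removed by the matching one.

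**Step 4: a right-skewed variable (assumed lognormal).** The log-scale SD is s = ln(r)/1.349. The share removed on the low side by the written rule is Φ{[ln(1.5r − 2.5) − 0.5 ln r]/s}. At r = 2, s = 0.693/1.349 = 0.514 and the argument is (−0.693 − 0.347)/0.514 = −2.02, which gives 2.2%.

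| r = Q3/Q1 | Removed, written rule | Removed, matching rule |
|---|---|---|
| 1.67 | 0% | 0% |
| 1.96 | 1.0% | 0% |
| 2.0 | 2.2% | 0% |
| 2.2 | 14.5% | 0% |
| 7/3 | 25.0% | 0% |
| 2.57 | 40.5% | 0% |
| 3.0 | 57.0% | 0% |

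These are shares of values within one visit and arm. They do not give the resulting shift in change to minimum, which would need patient-level data.

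**The case against.** The other side accepts that the sentence is reversed and argues that it matters little.

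- **It is a drafting slip with a plain intention.** The upper limit is the familiar fence, a negative haemoglobin limit would be conspicuous, and SAP Section 4 requires outputs to be validated and reviewed. A programmer may well code the usual fence. This is fair, but a validator may work from the same sentence. SAP Section 2 also gives the SAP primacy over the protocol and requires departures from it to be described in the study report, so silently coding something else is not a clean remedy.
- **The reach is small.** SAP Section 9.1 makes all safety summaries descriptive. The unfiltered table, shift tables, Grade 3/4 counts, box plots and listings are not stated to use the rule. This stands in full.
- **The large percentages are not tied to this trial.** Protocol Section 17.1 lists analytes that may be skewed, such as triglycerides, creatine kinase and C-reactive protein, but gives no spread for any of them. This stands: Step 4 is conditional on the ratio.
- **For haemoglobin and platelets the error keeps low values that the corrected fence could drop.** This is true on the assumed quartiles. It is a reason to read the filtered table beside the unfiltered one, not a reason to leave the formula wrong.
- **Cuts that differ by arm and visit come from taking quartiles by arm and visit.** This is correct, and it would remain after the fix.

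**Conclusion.** The point holds. As worded, the lower limit is the exact negative of the fence that matches the stated upper limit. For non-negative variables, that conclusion and the turning points at Q3/Q1 of 5/3, 7/3 and 5 need no distributional assumption. The haemoglobin and platelet limits rest on assumed quartiles, and the removal shares rest on an assumed lognormal shape.

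The harm arises only if the sentence is coded literally, and it stays within one descriptive repeat table. No efficacy result or adverse-event count depends on it. It should be fixed because the error is certain, the table was added specifically to deal with outliers, and correction is almost free. The mismatch over final values is a second, smaller defect in the same paragraph, and no convention settles it.

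**What to change.** In SAP 9.5, define an outlier as any value above the third quartile plus 1.5 times the IQR, or below the first quartile minus 1.5 times the IQR. Say once whether final values are filtered, and make the opening and closing sentences of the paragraph agree. Label the table as supplementary, to be read beside the unfiltered one.

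The cost is one sentence, one scope decision and a table label.

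The corrected fence has a drawback of its own: it can drop genuine low values. On the assumed quartiles it sits at 10 g/dL and 100 × 10⁹/L. Haemoglobin below 10 g/dL or platelets below 75 × 10⁹/L, both thresholds listed in Protocol Table 3, would therefore leave the filtered table. They would stay in the unfiltered table and listings, and in the planned plots: "Box plots of hemoglobin, platelets, and neutrophils will also be provided with dose interruption limits included as reference lines".

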17. APPENDICES

17.1. Clinical Laboratory Assessments

Hematology	Chemistry	Serum Pregnancy
Complete blood count Absolute neutrophil count Absolute eosinophil count Platelet count White blood cell count with differential Absolute reticulocyte count Hemoglobin A1c	Alanine aminotransaminase Albumin Alkaline phosphatase Amylase Aspartate aminotransaminase Total bilirubin Direct bilirubin Indirect bilirubin Blood urea nitrogen C-Reactive Protein (CRP) Calcium Carbon dioxide Chloride Creatinine Creatine kinase Glucose Lipase Total protein Phosphorus Potassium Sodium Uric Acid	Human chorionic gonadotropin (females of childbearing potential only)
Serology	Lipids (Fasted)	Other
Hepatitis B Surface Antigen (HBsAg) Hepatitis C Virus Antibodies (HCV Ab)	Total cholesterol Low-density lipoprotein High-density lipoprotein Triglycerides	Tuberculosis Thyroid stimulating hormone

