2. PURPOSE OF THE ANALYSES

This statistical analysis plan (SAP) provides a detailed description of the strategy and statistical methodology to be used for analysis of data from the CP543.3001 protocol, amendment 5.0, dated 28APR2021.

The purpose of the SAP is to describe the pre-specified statistical approaches to the analysis of study data prior to database lock. This analysis plan is meant to supplement the study protocol. If differences occur between analyses described in the SAP and the current protocol, those found in this SAP will assume primacy. Any deviations from this plan will be described in the Clinical Study Report (CSR).

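### SAP 9.5 misprints the lower outlier limit for the trimmed laboratory table, with its two terms reversed

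*SAP*

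**What the plan says.** SAP 9.5 summarises change from baseline to the minimum, maximum and final on-treatment value of each laboratory variable. It then adds a second pass: "This analysis will be repeated with outlying values removed from eligibility for minimum and maximum values". The IQR is Q3 minus Q1 and "will be calculated by visit and treatment group for each numeric parameter"; it is multiplied by 1.5. The upper limit is 1.5 × IQR plus Q3, which is the usual one. On the low side, a value "below 1.5 times IQR minus the first quartile will be considered an outlier". A flagged value "will be removed from eligibility for minimum, maximum, or final post-baseline values", which is wider than the opening sentence because it adds the final value.

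The scope is broad: "These analyses will be repeated for serum chemistry results, hematology results, and lipid results". Protocol 17.1 lists the panel, which includes "C-Reactive Protein (CRP) Calcium Carbon dioxide Chloride Creatinine Creatine kinase" and "Absolute eosinophil count". SAP section 13 says only that a further laboratory presentation was added because of outliers seen in blinded review. The protocol describes no trimmed laboratory table.

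**The concern.** Word order does not matter in a sum, so the upper limit is right however it is phrased. It does matter in a difference. Read as arithmetic, the lower limit has the wrong sign.

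A programmer who codes the sentence and one who silently corrects it will produce different tables from the same data. In the literal table, low outliers of tightly distributed analytes are never removed, so trimming is one-sided. For strongly skewed analytes, ordinary low and middling values are discarded. What is at stake is whether this one table can be interpreted and reproduced.

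**Working it through.** **Inputs.** The IQR definition, the multiplier 1.5, both limits and the by-visit, by-arm calculation come from SAP 9.5. The documents give no analyte distributions, so the spreads below are assumptions shown over a range. The plan states no figure to reproduce.

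**Algebra (no distribution needed, Q1 > 0).**

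- Printed limit: P = 1.5(Q3 − Q1) − Q1 = 1.5·Q3 − 2.5·Q1.
- Usual limit: C = Q1 − 1.5(Q3 − Q1) = 2.5·Q1 − 1.5·Q3. So P = −C.
- P > 0 when 1.5·Q3 > 2.5·Q1, that is Q3/Q1 > 5/3. Below that ratio P is negative, and no non-negative laboratory value can fall under it.
- P > Q1 when 1.5·Q3 > 3.5·Q1, that is Q3/Q1 > 7/3. More than a quarter of values are then flagged as low.
- P > Q3 when 0.5·Q3 > 2.5·Q1, that is Q3/Q1 > 5. More than three quarters are then flagged.

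Illustration with assumed quartiles: 13 and 15 give IQR 2, P = 3 − 13 = −10 and C = +10. Quartiles 0.6 and 3.0 give IQR 2.4 and P = 3.6 − 0.6 = 3.0, equal to Q3.

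**Share removed at the low end.** Assume a lognormal analyte with median 1 and no assay floor. Then Q1 and Q3 are exp(∓0.6745·s), where s is the log SD, and the share removed is Φ(ln P / s) when P > 0.

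| log SD | Q3/Q1 | P | Removed, printed | Removed, usual |
|---|---|---|---|---|
| 0.3 | 1.50 | −0.21 | 0% | 0% |
| 0.5 | 1.96 | 0.32 | 1.1% | 0% |
| 0.6 | 2.25 | 0.58 | 18.2% | 0% |
| 0.7 | 2.57 | 0.85 | 40.6% | 0% |
| 0.8 | 2.94 | 1.12 | 55.4% | 0% |
| 1.0 | 3.85 | 1.67 | 69.6% | 0% |
| 1.2 | 5.05 | 2.26 | 75.1% | 0% |

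Reading the phrase as 1.5 × (IQR − Q1) does not rescue it: 18.5% are removed at log SD 0.7 and 63.6% at 1.0.

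**Effect of an assay floor.** SAP section 4 analyses a result reported as below a limit as that limit. If more than 25% of values sit at the floor, Q1 equals the floor. Once Q3/Q1 is then under 7/3, P lies below the floor and nothing is removed.

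- Log SD 0.7, 30% at the floor: Q1 = 0.693, Q3 = 1.603, ratio 2.31, P = 0.67. Removed: 0%, against 41% with no floor.
- Log SD 1.0, 40% at the floor: Q1 = 0.776, Q3 = 1.963, P = 1.00. Removed: 50%.
- Log SD 1.0, 45% at the floor: Q1 = 0.882, ratio 2.23, P = 0.74. Removed: 0%, against 70% with no floor.

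**What the literal table would show.** Simulated arm of 210 (the planned 12 mg arm), seven post-baseline visits (Weeks 2, 4, 8, 12, 16, 20 and 24), no drug effect, log SD 1.0, no floor, half the log variance within patient. Limits are set by visit and baseline is left untrimmed. Mean change to minimum, in units of the analyte median, is about −1.1 untrimmed and −1.1 under the usual rule. Under the printed rule it is about zero (+0.02 to +0.05 across runs). About 147 of 210 patients keep any eligible value. Counting both ends, about 76% of values are removed as printed and 7.8% under the usual rule.

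**The case against.** The strongest reply is that this is a slip of word order and nothing more. The SAP names the IQR method, gives the multiplier and prints the upper limit correctly, so any statistician will recognise what was meant. SAP section 4 also requires outputs to be validated and reviewed. A haemoglobin limit near −10 g/dL, or most values of one analyte flagged, would be conspicuous. This largely stands: the usual limit is very probably intended. It does not make the printed rule right. Mock tables are attached to the SAP but not visible here, so a footnote in one of them might state the rule correctly. The claim is only that no visible text does.

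Three stronger readings are tempting, and the documents do not support them.

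- A reader might infer that analytes such as CRP, creatine kinase or eosinophils will lose most of their values. The documents give no spreads, and the SAP section 4 rule for results below an assay limit can bring the loss to zero.
- A reader might infer that low haemoglobin or platelet values would be hidden. The misprint keeps such values. It is the intended rule that can trim them from this table, which is a property of trimming and not a harm of the error.
- A reader might infer that the SAP's clause "those found in this SAP will assume primacy" obliges the programmer to code the misprint. That clause settles differences from the protocol, and the protocol has no trimmed table to differ from.

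**Conclusion.** The point holds as a drafting error: the lower limit is wrong as written. The sign reversal and the thresholds 5/3, 7/3 and 5 follow from the text alone, given positive quartiles and non-negative values. The removal shares of 18%, 41% and 70% at log SD 0.6, 0.7 and 1.0 are illustrations. They assume literal coding, a lognormal shape and no assay floor. At log SD 0.5 or less the loss is about 1% or none.

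Severity is minor. The error touches one supplementary descriptive table. The untrimmed summary, shift tables, counts of potentially clinically significant values, box plots against the interruption limits and listings do not use the rule. SAP 9.1 makes all safety summaries descriptive, so no efficacy or safety conclusion depends on this table.

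**What to change.** In SAP 9.5, define an outlier as a value above Q3 + 1.5 × IQR or below Q1 − 1.5 × IQR. In the sentence that introduces the repeat analysis, name the minimum, maximum and final values, so that it agrees with the sentence that carries out the removal. If a mock table repeats the rule, check it against the corrected text.

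The cost is two edited sentences. No data, other output or analysis decision changes.

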8.3. Patient Withdrawal Criteria

For all patients, it is the intent that patients who discontinue study medication (at any time) for any reason will continue to be followed for all protocol-planned study visits through the completion of the 24-week treatment period, and will have all endpoints (including efficacy) collected accordingly.

The Investigator, Sponsor, or its designee may decide a patient should discontinue treatment at any time and for any reason. In addition, patients will discontinue randomized treatment if they:

- Experience an intolerable adverse event, including but not limited to bone marrow related events characterized by protocol specified hematologic abnormalities, or a \geq Grade 3 cardiac event, or a \geq Grade 4 (other) adverse event (CTCAE v5.0 criteria) considered possibly related to study drug. Because laboratory abnormalities can occasionally occur that do not in themselves pose an unacceptable risk to subject safety (e.g., CK elevations with exercise, laboratory errors or artifacts), the occurrence of a \geq Grade 4 laboratory abnormality, or any laboratory abnormality of concern to the Investigator, will be discussed with the Medical Monitor and a determination will be made, based on a reassessment of risk-benefit for the subject, whether the subject should discontinue randomized treatment. Documentation on the determination will be maintained in the study files;
- Require a medication that is prohibited by the protocol. However, under certain circumstances, and in consultation with the Medical Monitor, short-term use of a prohibited medication may not necessitate withdrawal of treatment when its use is unlikely to unfavorably alter the risk-benefit of subject participation;
- In the opinion of the Investigator, have any medically appropriate reason;
- Become pregnant;
- Have a serious adverse event associated with a SARS-CoV-2 infection;

- The Investigator believes that further treatment is undesirable or the risk-benefit profile has become unfavorable.

Furthermore, dose interruptions lasting more than 21 days may require treatment discontinuation on a case by case basis following consultation with the Medical Monitor.

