are those in which the baseline value is not PCS and the post-baseline value is PCS. The number and percentage of patients with treatment-emergent PCS laboratory values will be summarized by treatment group for each clinical laboratory variable.

Vital Signs

The mean change from baseline to each scheduled assessment will be summarized descriptively by treatment group for each vital sign variable specified in this protocol.

Baseline will be defined as the last vital sign value obtained before the first dose of study drug on Day 1; if Day 1 values are unavailable, then values obtained at the Screening Visit will be used.

The number and percentage of patients with at least 1 PCS vital sign value will be summarized descriptively.

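### For laboratory parameters graded independently of baseline, the treatment-emergent PCS table in SAP 9.5 does not count worsening from Grade 3 at baseline to Grade 4 on treatment

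*SAP*

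**What the plan says.** The third laboratory presentation in SAP 9.5 is a count, by treatment group, of patients with treatment-emergent PCS values. Grading uses CTCAE version 5.0 on the numeric result alone. The SAP states that "PCS values are defined as those that meet Grade 3 or Grade 4 toxicity criteria".

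The treatment-emergent rule has two branches:

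- The first opens with "For laboratory parameters whose CTCAE grading is independent of baseline criteria" and continues that "treatment-emergent PCS laboratory values are those in which the baseline value is not PCS and the post-baseline value is PCS".
- The second covers parameters whose grade is itself defined relative to baseline. There, "any post-baseline grading of Grade 3 or Grade 4 will be considered treatment-emergent".

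Protocol 12.4.7 has a single rule without the split: treatment-emergent PCS values "are those in which the baseline value is not PCS and the post-baseline value is PCS". Where the two documents differ, SAP Section 2 says that "those found in this SAP will assume primacy", so the two-branch version governs.

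Laboratory baseline is the pre-dose Day 1 value, with Screening as the fallback.

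**The concern.** PCS pools Grades 3 and 4, and the first branch asks only whether the patient crossed into that pool. Someone already in it at baseline cannot be counted, even if the value moves to the worse of the two grades on treatment.

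Elsewhere the protocol keeps the two grades apart. Protocol 8.3 says that a "Grade 4 laboratory abnormality, or any laboratory abnormality of concern to the Investigator, will be discussed with the Medical Monitor" to decide whether treatment should stop. Protocol Table 3 handles neutrophil counts in the Grade 3 and Grade 4 ranges differently.

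The PCS table is the plan's one by-arm laboratory count of severe toxicity that does not depend on clinical judgement. As a count of severe worsening, its omission runs in one direction only, towards too few events.

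**Working it through.** The plan states no figure to reproduce here. The check is an enumeration of the rule, followed by a search for another output that would show the same event.

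**Step 1. Apply each branch to every baseline grade.** Inputs: PCS means Grade 3 or 4. Branch 1 counts if baseline grade < 3 and post-baseline grade ≥ 3. Branch 2 counts if post-baseline grade ≥ 3.

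| Baseline grade | Branch 1 (independent of baseline): post-baseline 3 / 4 | Branch 2 (dependent on baseline): post-baseline 3 / 4 |
|---|---|---|
| 0, 1 or 2 | counted / counted | counted / counted |
| 3 | not counted / **not counted** | counted / counted |
| 4 | not counted / not counted | counted / counted |

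The bold cell is the point. The other uncounted cells in Branch 1 involve no rise in grade.

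**Step 2. Look for the event in the other planned outputs.**

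- *Shift tables (SAP 9.5).* The categories are below, within and above the reference range. Grade 3 to Grade 4 in the same direction stays in one category.
- *Change summary (SAP 9.5).* The "change from baseline to the minimum post-baseline value, maximum post-baseline value, and final on-treatment value will be summarized". The value contributes, but this is a group summary without grades. The SAP also repeats it with values beyond 1.5 times the interquartile range removed, which could drop such a value from the repeat.
- *Listings and box plots (SAP 9.5).* Every result is listed, and hemoglobin, platelets and neutrophils are plotted against the interruption limits. Neither gives a count of grade worsening by arm.
- *Adverse event tables (SAP 9.3).* Under Protocol 10.12 and 11.1 an abnormal value becomes an adverse event if it is clinically significant, leads to discontinuation from the study, or is judged to need treatment, dose interruption or other intervention. A worsened value that meets none of these conditions does not reach these tables.

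**Step 3. Ask whether a Grade 3 baseline can occur.** Exclusion criteria 12 to 16 apply at Screening, which may be up to 28 days before Day 1. They cover thyroid stimulating hormone, platelets, neutrophils, hemoglobin, hemoglobin A1c, liver tests and renal function. Criterion 13 is open-ended but gives no threshold beyond its named items. Creatine kinase, lipids, amylase and lipase are measured (Protocol Appendix 17.1) and have no named limit. Protocol 8.3 itself anticipates creatine kinase elevations after exercise.

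For neutrophils the room is narrow. Counts of 1.5 x 10⁹/L or less are excluded at Screening, while Table 3 puts Grade 3 at 0.5 to 1 x 10⁹/L. A Day 1 value in that range would need a large fall before any drug was taken.

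**Step 4. Size.** The documents give no frequency of Grade 3 baselines and do not say which parameters fall in which branch, so no count follows from them. For scale only, assume that 0.5% to 1% of the 210 + 350 = 560 active patients have a Grade 3 baseline in an affected parameter. That is 0.005 x 560 = 2.8 to 0.01 x 560 = 5.6 patients at risk. If, again by assumption, 10% of them progressed to Grade 4, the table would miss 0.28 to 0.56 patients.

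**The case against.** The strongest case on the other side is that this is a usual threshold-crossing definition, applied alike to all arms including placebo, in safety summaries that SAP 9.1 makes descriptive without hypothesis tests. Grade 4 values have other routes to attention: the Protocol 8.3 discussion is triggered by the value itself, whatever the table counts. All of this stands, and it is why the point is minor. It does not supply the missing count.

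Three stronger readings are tempting, and the documents do not support them.

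- *Such a patient is never counted.* A reader might infer this from the rule quoted without its opening qualifier. The second branch counts Grade 3 to Grade 4, and the adverse event tables can count the event in either branch. Take neutrophils falling from 0.9 to 0.4 x 10⁹/L: Table 3 calls for immediate interruption, Protocol 11.1 makes an abnormality judged to require interruption an adverse event, and SAP 9.3 tabulates adverse events by severity and by interruption.
- *Three to six patients would be missed.* The 2.8 to 5.6 in the working is an assumed pool at risk. Reading it as missed events would also assume that every such patient progresses.
- *The two branches contradict each other.* Where the grade is already relative to the patient's own baseline, a further baseline condition is not needed. The split is a deliberate refinement of the protocol's rule, and the difference between the branches is not an error.

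**Conclusion.** The point holds within its limits. For baseline-independent parameters, worsening from Grade 3 to Grade 4 cannot enter the treatment-emergent PCS table, and no other planned numeric laboratory count by arm shows it. This follows from the wording of SAP 9.5 and needs no assumption.

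The practical size does rest on assumptions: how often a Day 1 value is already Grade 3, how often it then worsens, and which parameters CTCAE grades independently of baseline. The documents give none of these. The effect is probably small, least likely for the screened hematology parameters and most plausible where no screening limit is named. Efficacy conclusions are untouched. This is an inexpensive improvement to a safety table, not a flaw that threatens the trial's interpretation.

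**What to change.** In SAP 9.5, change the baseline-independent branch only: a treatment-emergent PCS value is any post-baseline Grade 3 or 4 value with a grade higher than the patient's baseline grade. Every event that branch now counts is kept, because a baseline of Grade 0, 1 or 2 is always below Grade 3 or 4. Grade 3 to Grade 4 is added.

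Leave the baseline-dependent sentence as it is. Applying the new condition there would drop Grade 3 to 3 and Grade 4 to 4 values that are counted today, and would need a baseline grade that the SAP does not define for those parameters.

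SAP 9.6.1 defines PCS vital signs by reference to this section, so confirm that the revised wording carries over as intended. Record the departure from Protocol 12.4.7 in SAP Section 13.

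The cost is one sentence, one programming condition, that check and a line in Section 13. If the definition is to stay, a CTCAE grade-shift table by arm would show the same information at the price of one more output.
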